**I. Primary Objectives**

1. To estimate the patterns of antidepressant (AD) prescription at hospital discharge among a population of non-contraindicated stroke patients.
2. To estimate the associations between antidepressant use (any vs. none) and outcomes (home time, all-cause mortality, stroke readmissions, cardiovascular readmissions, and depression-related hospitalizations following discharge).
3. Repeat analyses for patients with SSRI information (SSRI vs. other AD).
4. To examine associations between AD and outcomes in subgroups based on age (80/90), sex, race (white/non-white), NIH stroke scale (<16/≥16), and history of depression.
5. To estimate patterns of AD prescription (AD vs none and SSRI vs other AD) at hospital discharge among prospectively enrolled PROSPER patients with ischemic stroke discharge
6. To examine associations between antidepressant use (any vs.none) and patient reported outcomes following ischemic stroke discharge
7. To examine associations between types of antidepressant used (SSRI vs. other AD) and patient reported outcomes.

**Study Population *N Patients* *N Sites* % Remained**

1. Starting Population: All PROSPER (GWTG-Stroke linked to CMS\*) patients enrolled in a fully-participating GWTG hospital with a final clinical diagnosis of acute ischemic stroke in year 2014 104,423 1,436
2. Exclusions:
 

1) Patients FFS ineligible	-5,582	-2	94.7%
2) Patients discharged before April 2014	-23,467	-15	76.3%
3) Patients left AMA/discharge disposition UTD/missing	-255	-0	99.7%
4) Patients transferred out	-1,486	-4	98.0%
5) In-hospital deaths	-4,148	-2	94.4%
6) Discharge AD not documented (historic and new)	-31,801	-383	54.2%
7) Patients with AD contraindications	-8,507	-7	77.4%
	=29,177	=1,023	
3. Final Study Population: 29,177 patients from 1,023 hospitals  
Study period: Apr 1, 2014 – Dec 31, 2014

\* Linkage to CMS implies that patients are at age of 65 or older, linked with first admission

**Table.** New AD variable by historic AD variable check in the IS study population.

Antidepressant Medication(s) At Discharge (New)	Antidepressant Medication(s) At Discharge (Historic)			
	Missing	1= Yes	2 = No/ND	Total
. = Missing	0 0 0 0	6075 20.82 27.23 99.72	16234 55.64 72.77 99.71	22309 76.46
1 = Yes, SSRI	1063 3.64 99.16 15.63	9 0.03 0.84 0.15	0 0 0 0	1072 3.67

Antidepressant Medication(s) At Discharge (New)	Antidepressant Medication(s) At Discharge (Historic)			
	Missing	1= Yes	2 = No/ND	Total
2 = Yes, any other antidepressant class	438 1.50 98.21 6.44	8 0.03 1.79 0.13	0 0 0 0	446 1.53
3 = No/ND	5302 18.17 99.10 77.94	0 0 0 0	48 0.16 0.90 0.29	5350 18.34
Total	6803 23.32	6092 20.88	16282 55.80	29177 100

Color code: AD Yes patients, AD No patients

## II. Variables

## 1. Primary exposure variable

Any antidepressant prescription at hospital discharge (yes vs. no, derived from a combination of historic and revised antidepressant variables)

- Historic AD variable: AD Yes / AD No
- New AD variable: Yes, SSRI / Yes, other AD class

SSRI (selective serotonin reuptake inhibitors) are defined as any of the following: Citalopram (Celexa), Escitalopram (Lexapro), Fluoxetine (Prozac), Paroxetine (Paxil, Pexeva), Sertraline (Zoloft). Other antidepressant therapy will be defined as all other non-SSRI antidepressants. SSRI analyses will be limited to patients with complete data on the new AD variable.

AD	Frequency	Percent	SSRI	Frequency	Percent
Yes	7,593	26.02	Yes, SSRI	1,072	70.62
No	21,584	73.98	Yes, other AD	446	29.38
Total	29,177	100	Total	1,518	100

Variable	Level	Overall (N=29177)	AD YES (N=7593)	AD NO (N=21584)	P-value+
History of depression	Yes	4341 14.88	3309 43.58	1032 4.78	<.0001
	No	24836 85.12	4284 56.42	20552 95.22	
AD prior to admission	Yes	6432 22.28	5678 75.57	754 3.53	<.0001
	No	22437 77.72	1836 24.43	20601 96.47	
	Missing	308 1.06	79 1.04	229 1.06	

Variable	Level	Overall (N=1518)	SSRI YES (N=1072)	SSRI NO (N=446)	P-value+
History of depression	Yes	667 43.94	474 44.22	193 43.27	0.7361
	No	851 56.06	598 55.78	253 56.73	
AD prior to admission	Yes	1125 74.75	800 75.33	325 73.36	0.4238
	No	380 25.25	262 24.67	118 26.64	
	Missing	13 0.86	10 0.93	3 0.67	

## 2. Other variables

Demographics: Age, race, gender, insurance status, medical history (depression, stroke, TIA, DM, CAD, AF, HF, HTN, PVD, smoking)

Presentation variables: EMS transport, ambulatory status, initial NIHSS, prior antidepressant use

In-hospital variables: Dysphagia screening, DVT prophylaxis, t-PA, t-PA date/time, VTE interventions, documented DVT/PE, antithrombotics by day 2

Discharge variables: Discharge disposition, ambulatory status at discharge, ICD-9 discharge diagnosis, Antiplatelet/anticoagulant/HTN/AD meds, stroke education, smoking cessation, assessment for rehabilitation services

Hospital variables: Primary stroke center; comprehensive stroke center, teaching status, hospital bed size, rural location, region, annual volume of IS admissions

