### 3. Outcomes/Endpoints

#### Primary:

- Home-time: Total number of days spent alive and outside of a hospital, skilled nursing facility, or inpatient rehabilitation facility since discharge

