#### Secondary:

- All-cause mortality: Ascertained on the basis of the death date recorded in the denominator/vital status file.
- All-cause readmission: Readmission date will be ascertained from the inpatient institutional file.
- Stroke/TIA readmission: Readmission date will be ascertained from the inpatient institutional file and determined by ICD-9-CM principal diagnoses code of 430, 431, 432.x-435.x, and 436 on the inpatient claim. Ischemic stroke and hemorrhagic stroke will be analyzed separately.
- Cardiovascular readmission: CV Readmission date will be ascertained from the inpatient institutional file and determined by DRG 104–112, 115–118, 121–145, 479, 514–518, 525–527, 535, 536, and 547–558 on the inpatient claim.
- Non-cardiovascular readmission: All readmissions not meeting CV readmission criteria.
- Depression related readmission: Completed suicide, suicide attempt or major depressive episode (major depressive disorder [296.2, 296.3, 296.5, 298.0, or 311], completed suicide/suicide attempt [E950-E959\*], suicide ideation [V62.84], or suicide tendencies [300.9])

\*Given the potential for under-capture of completed suicides and suicide attempts, depression-related admission outcomes will be considered exploratory (reference: [http://www.minsentinel.org/work\\_products/HealthOutcomes/MS\\_HOI\\_SuicideReport.pdf](http://www.minsentinel.org/work_products/HealthOutcomes/MS_HOI_SuicideReport.pdf))

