Hospital characteristics				
Teaching status				
Rural location				
Region				
Primary Stroke Centers				
Comprehensive Stroke Centers				
Hospital size, mean (SD)				
Annual IS admission volume, mean (SD)				

All numbers presented are proportions of patient in the study population, unless specified otherwise.

\* P-values from chi-squared tests for independence for categorical variables and Wilcoxon rank sum tests for continuous variables

## 2. Objective 2

**Aim:** To estimate the associations between antidepressant use (any vs. none) and outcomes (home time, all-cause mortality, all-cause readmission recurrent stroke [ischemic, hemorrhagic], cardiovascular rehospitalization, and depression-related hospitalization [suicidality or major depressive episode] following discharge).

**Analysis:** Because patients who receive AD may differ from those who do not on important baseline and clinical characteristics that may affect the likelihood of adverse events, we will use inverse probability of treatment weighting (IPW) when assessing treatment effects. IPT weighting will be accomplished in two steps: First, we will use a logistic regression model to assign a probability of treatment selection to each patient based on the distribution of a defined set of covariates (listed above). The binary outcome for the selection model will be AD treatment (Y/N). In the second step, we will weight subject by the inverse of this assigned treatment probability, resulting in a pseudo-randomization of patients to AD vs. no AD treatment. The distribution of baseline patient characteristics for each treatment group will be assessed after weighting to determine adequacy of the selection model.

Following IPW, we will compare primary and secondary endpoints between treatment groups. Unadjusted rates of all-cause mortality, all-cause readmission, CV readmission, depression-related admission and stroke/TIA readmission will be examined using a Cox proportional hazards model with AD use as the single independent variable. Adjusted event rates will then be estimated using the same model with IPW included for each subject. Within-hospital clustering will be accounted for using robust estimator approach.

Home time will be examined first as a continuous variable in a linear regression model and then as a dichotomous outcome in an IPW-weighted logistic regression model, using 100% of time spent at home over 1 year as the primary outcome of interest.

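### No covariate listed for the selection model measures pre-stroke home-time or prior hospital, nursing or rehabilitation use, although the cohort is linked to Medicare claims

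*SAP*

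**What the plan says.** Under Objective 2 the SAP uses inverse probability weighting. A logistic model will "assign a probability of treatment selection to each patient based on the distribution of a defined set of covariates (listed above"). Two lists precede that sentence and could be meant.

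- **Other variables (section 2 under Variables).** Demographics, insurance and "medical history (depression, stroke, TIA, DM, CAD, AF, HF, HTN, PVD, smoking"); then "Presentation variables: EMS transport, ambulatory status, initial NIHSS, prior antidepressant use"; then in-hospital, discharge and hospital items.
- **Table 1.** This overlaps with the first list and adds carotid stenosis, dyslipidemia, other medications before admission, onset-to-arrival time and laboratory values.

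The primary endpoint is defined as "Total number of days spent alive and outside of a hospital, skilled nursing facility, or inpatient rehabilitation facility since discharge". The protocol (Study Outcomes) places home-time among the outcomes taken from the linked GWTG-Stroke and CMS data.

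The SAP mentions claims for linkage and fee-for-service eligibility (Study Population) and for ascertaining secondary outcomes, for example "Readmission date will be ascertained from the inpatient institutional file". It defines no look-back period before the index admission.

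**The concern.** Weighting balances what is in the selection model and whatever is correlated with it, and no more. Someone already moving in and out of hospital or nursing care before the stroke is likely to spend fewer days at home afterwards, and may also be more likely to be discharged on an antidepressant. If so, part of any difference between the groups in home-time, mortality or readmission reflects the patients' earlier state and not the prescription.

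The baseline level of an endpoint is usually among its strongest predictors. Here it could be computed with the same day count that the endpoint already needs, run backwards from admission. Leaving it out means giving up a relevant covariate that the linked data may already be able to supply.

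**Working it through.** **1. The cohort figure reproduces.** From the Study Population table: 104,423 − 5,582 = 98,841; − 23,467 = 75,374; − 255 = 75,119; − 1,486 = 73,633; − 4,148 = 69,485; − 31,801 = 37,684; − 8,507 = 29,177, as stated. The groups also reproduce from the cross-table of new and historic variables: 6,075 + 1,072 + 446 = 7,593 on an antidepressant and 16,234 + 5,350 = 21,584 not.

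**2. Search of the two lists.**

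| Item | Other variables | Table 1 |
|---|---|---|
| Pre-stroke home-time | no | no |
| Prior hospital admissions | no | no |
| Prior skilled nursing or rehabilitation stay | no | no |
| Pre-stroke residence or function | no | no |
| Any item identified as claims-derived | no | no |

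The finding does not depend on which list is meant.

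**3. Whether anything else fills the gap.** The baseline Rankin Scale in the protocol belongs to the prospective component. The restriction to antidepressant-naive patients under Objective 3 applies to cumulative incidence curves and their log-rank and Gray tests. No weighting is described there, and home-time is not among those analyses. The protocol promises pre-specified sensitivity analyses, but the SAP contains none for unmeasured confounding.

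**4. A yardstick for precision.** The SAP tabulates prior antidepressant use by group. Excluding 308 patients with that item missing leaves 28,869. Weighting on this one item alone:

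- P(treated | prior use) = 5,678 / 6,432 = 0.883; P(treated | no prior use) = 1,836 / 22,437 = 0.082.
- Effective sample size = (sum of weights)² / (sum of squared weights).
- Antidepressant group: 28,869² / (5,678/0.883² + 1,836/0.082²) ≈ 2,961, using unrounded probabilities.
- No-antidepressant group: 28,869² / (754/0.117² + 20,601/0.918²) ≈ 10,509, likewise.
- SE = SD × √(1/2,961 + 1/10,509) = 0.0208 × SD.

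The documents give no SD for home-time. For an assumed 110 to 130 days, the 95% half-width is 1.96 × 0.0208 × SD, about 4.5 to 5.3 days.

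**5. Illustrative bias.** Bias in days = (difference between weighted groups in the share of patients with pre-stroke institutional days) × (home-time deficit of such patients). Neither input is in the documents. Assuming 3 to 10 percentage points and 40 to 80 days:

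- low: 0.03 × 40 = 1.2 days, and 1.2 / 5.3 ≈ 0.2 half-widths;
- high: 0.10 × 80 = 8 days, and 8 / 4.5 ≈ 1.8 half-widths.

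**6. Look-back available.** One exclusion is "Patients discharged before April 2014", so the earliest index discharge is 1 April. From 1 January to 1 April 2014 is 31 + 28 + 31 = 90 days. If only 2014 claims are held, a patient discharged on 1 April after a stay of L days has 90 − L days before admission. A 90-day window is therefore out of reach for the earliest patients. A 60-day window is met by any stay of up to 30 days.

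**The case against.** The strongest reply is that pre-stroke status is not unadjusted. Medical history, prior antidepressant use, other prior medications, insurance, NIHSS, ambulation and discharge disposition are all listed, and each may carry some information on frailty or on early home-time. What matters is the imbalance left after all of them, and on that the documents are silent. This stands, and it is why no size can be claimed. It does not remove the omission, because none of these items records earlier institutional use.

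Four stronger readings are tempting but unsupported.

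- **That every covariate is a registry item from the index stay.** The SAP gives no source for each variable. The hospital items ("Hospital variables: Primary stroke center; comprehensive stroke center, teaching status, hospital bed size, rural location, region, annual volume of IS admissions") are site-level, and the source of insurance status and discharge diagnosis is open.
- **That the gap in prior antidepressant use (75.57% against 3.53%) shows residual confounding.** It is an unweighted difference in a covariate already listed, which weighting is meant to remove. The relevant question is whether frailty differs between groups within levels of prior use, and no data bear on it.
- **That the primary result would shift by the days shown.** Those figures rest on assumed inputs. The half-width uses one weighting variable and ignores hospital clustering; the full model would probably widen it and so reduce the ratio. The SAP also names all time at home over one year, analysed by logistic regression, as the main outcome of interest. The illustration says nothing on the odds-ratio scale.
- **That look-back claims are certainly in hand.** The SAP describes index strokes in 2014 linked at first admission. It does not say that earlier claims are held.

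**Conclusion.** The point holds as an omission from the covariate list. Neither list includes pre-stroke home-time or prior hospital, nursing or rehabilitation use, and nothing else in the protocol or SAP supplies them. The weighted comparisons of home-time, mortality and readmission remain open to confounding by pre-stroke frailty that the listed items capture only in part.

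The documents establish neither the size nor the direction of that confounding. Under the stated assumptions it could run from negligible to large enough to create or hide a nominally significant difference in days. That range shows that the question is worth settling; it does not estimate the bias. I rate this a cheap improvement to an observational analysis, not a demonstrated error.

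**What to change.** Add to the Other variables section and to the selection model, from linked claims before the index admission:

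- pre-stroke home-time, computed with the same day count as the endpoint;
- number of inpatient stays;
- any skilled nursing or inpatient rehabilitation stay.

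Use one fixed look-back for everyone: 12 months if earlier claims are held, otherwise a window that nearly all patients can have from 2014 claims alone, such as 60 days. State the fee-for-service coverage required. Patients newly 65 or newly in fee-for-service need a category for incomplete look-back or a sensitivity run.

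Show the new variables in Table 1 before and after weighting. Also report, with its confidence interval, the weighted group difference in pre-stroke home-time when the current list alone is used. A discharge prescription cannot change days before admission, so a clear difference would point to residual confounding. The check is partial: it carries sampling error and covers this dimension only, so a result near zero would not clear other confounders.

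The cost is SAP wording and some programming, with incomplete look-back for some patients. It stays low only if pre-admission claims are already held, and the sponsor should confirm that first.

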Most research for stroke is aimed at practitioner-centered treatment in acute care settings. Limited evidence is available to guide stroke survivors to make informed decisions balancing the benefits and risks for improving stroke recovery and prevention of recurrent stroke or complications based on individual preferences, needs, and values. Many stroke survivors express concerns about long-term medication safety and effectiveness, especially given the different characteristics among patients. Many wonder which medications improve (or worsen) time at home, quality of life, activities of daily living, functional status, fatigue, depression or anxiety. Other questions include which medication should be taken among many choices, for how long and the trade-offs regarding long-term health versus potential adverse effects.

Objectives

The overall goal of PROSPER is to create a national, sustainable model to improve decision-making and patient-centered stroke outcomes through comparative effectiveness research. The American Heart Association (AHA), American Stroke Association (ASA), its volunteers, and the Duke Clinical Research Institute (DCRI) propose to address existing evidence gaps and develop the requested data on the range of clinical outcomes that may be experienced by stroke survivors. To achieve these goals, we will link the nation's largest stroke registry, the AHA Get With The Guidelines-Stroke program and nationwide Medicare claims data, coupled with telephone interviews for longitudinal treatment and downstream patient-reported outcomes. We will then conduct series of comparative effectiveness and safety studies that will inform existing and emerging stroke treatment options in order to improve outcomes most important to stroke patients.

Patient-centered Research into Outcomes Stroke patients Prefer and Effectiveness Research (PROSPER) is organized under three specific aims:

Aim 1: To develop a national platform to identify outcomes most desired and prioritized by patients as well as evaluate treatment options.

Aim 2: To apply this platform to conduct comparative effectiveness studies on outcomes as prioritized by patients and other stakeholders in the following treatment areas:

- a) Oral Anticoagulation
- b) Statin therapy
- c) Anti-depressant therapy

Aim 3: To design, evaluate and implement novel decision aids from our comparative effectiveness studies that empower stroke survivors to more effectively make treatment decisions.

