At hospitalization, study personnel will screen for eligible patients according to the PROSPER study inclusion/exclusion criteria. Study eligibility will then be confirmed via medical record review prior to discharge. Sites will be trained and required to screen subjects according to the screening procedures for GWTG-Stroke. Those who choose to participate will be consented by site staff before discharge home. Throughout enrollment, the PROSPER team will review demographics and characteristics of patients to ensure a diverse population.

The follow-up Contact form will also be completed by the study coordinator at the time of enrollment using information provided by the patient at the time of enrollment. It includes comprehensive follow-up information for both the patient and two alternative contacts. Primary physician contact information will also be documented in the event that medical records are needed to be obtained. To assist with obtaining additional medical records a medical release form will also be obtained.

Baseline Data Collection

Baseline data collection will be completed by the study coordinator at the time of hospitalization, using primarily inpatient medical records. All baseline data must be collected and submitted for every subject within 7 days of enrollment. All data collection forms must be clearly labeled with the site-assigned unique study identifier.

- The GWTG – Stroke data collection form (Appendix A) will be the primary baseline data source for the acute ischemic stroke admission in GWTG hospitals. These in-hospital variables (required variables printed in bold font) include the following: demographics, medical history, NIHSS on admission, presentation information, stroke symptoms, evaluation, and diagnoses, acute therapies, including thrombolytics and DVT prophylaxis, discharge medications/interventions for recurrent stroke risk reduction, treating physician specialty, and discharge status and destination.
- The GWTG acute ischemic stroke hospitalization data will be augmented by the addition of the Rankin Scale
- Subject consent
- Subject Contact /demographics/stroke form
- Medical Release
- Discharge Medications

CONFIDENTIAL

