## III. Analysis Tasks

### 1. Objective 1

**Aim:** To describe patient and hospital characteristics in the study population by discharge AD.

**Analysis:** Patient characteristics including demographics, medical history, initial vital signs, lab results and hospital characteristics will be described for the study population by discharge AD use. Categorical variables will be presented as proportions, and continuous variables will be presented as mean (standard deviation). We will compare the respective distributions of baseline characteristics among patients receiving 1) Any AD vs. no AD, and 2) SSRI vs. non-SSRI. Differences between groups will be evaluated using chi-square tests for categorical variables and Kruskal-Wallis tests for continuous variables.

**Output:** [Table 1](#) (patient baseline table)

**Table 1A.** Baseline characteristics of GWTG-Stroke-CMS patients by discharge AD use.

Variables	AD at Discharge	No AD at Discharge	Standardized differences, %	P-value*
------------------	------------------------	---------------------------	------------------------------------	-----------------

**Table 1B.** Baseline characteristics of GWTG-Stroke-CMS patients by discharge AD type.

Variables	SSRI at Discharge	Other AD at Discharge	Standardized differences, %	P-value*
------------------	--------------------------	------------------------------	------------------------------------	-----------------

(Detailed table entries on next page)

**Table 1.** Baseline characteristics of GWTG-Stroke-CMS patients\* overall and by discharge AD.

Variables	AD at Discharge	No AD at Discharge	StdDiff, %	P-value*
Demographics				
Age, year, mean (SD)				
Gender: Female				
Race/Ethnicity				
Medical History				
Depression				
Atrial Fibrillation				
Stroke/TIA				
CAD/MI				
Carotid Stenosis				
Diabetes Mellitus				
PVD				
Hypertension				
Smoker				
Dyslipidemia				
Heart Failure				
Medications prior to admission				
Antidepressants				
Anti-hypertensives				
Cholesterol-reducers				
Diabetic medications				
Presentation				
EMS transport				
Initial NIHSS				
Onset to arrival times (Prehospital delay)				
<2 hours				
2-4 hours				
>4 hours				
Symptoms resolved at time of presentation				
Ambulatory status on admission				
Labs				
Body Mass Index, mean (SD)				
Systolic blood pressure, mean (SD)				
Hemoglobin A1C, mean (SD)				
LDL-C, mean (SD)				

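### Statin therapy at discharge is absent from the covariates for the antidepressant weighting model, which leaves the AD vs none comparison open to a small residual confounding that the balance check would not show

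*SAP*

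**What the plan says.** SAP, Analysis Tasks, Objective 2: a logistic model assigns each patient a probability of treatment "based on the distribution of a defined set of covariates (listed above"), and the inverse of that probability is the weight. No separate propensity list is given. The list that this points to is SAP, Other variables:

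- Discharge drugs and services: "Antiplatelet/anticoagulant/HTN/AD meds, stroke education, smoking cessation, assessment for rehabilitation services".
- History: "medical history (depression, stroke, TIA, DM, CAD, AF, HF, HTN, PVD, smoking"). Dyslipidemia is not included.
- "Presentation variables: EMS transport, ambulatory status, initial NIHSS, prior antidepressant use". Prior antidepressant use is the only pre-admission drug.

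Table 1 of the SAP also stands before Objective 2. Its rows include "Cholesterol-reducers" under medications before admission, dyslipidemia and LDL-C. It has no row for any discharge drug. Discharge statin use appears nowhere in the SAP.

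The protocol, under Objectives, Aim 2, lists "b) Statin therapy" as one of three treatment areas to be compared. Its Study Outcomes section gives one candidate list for all three areas: home-time, death, and stroke/TIA, all-cause, cardiovascular and bleeding readmission. Under Baseline Data Collection, the registry form is said to hold "discharge medications/interventions for recurrent stroke risk reduction".

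**The concern.** The protocol treats statin therapy as a possible cause of home-time, death and readmission. These are also the SAP's primary endpoint and its main secondary endpoints; depression-related readmission is specific to the SAP and is not part of this point. Statin and antidepressant prescriptions are settled at the same discharge. They could go together, where prescribing is more complete, or apart, where frailty or pill burden limits the number of drugs.

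The SAP already lists three other drug classes from that discharge (antiplatelet, anticoagulant, antihypertensive) and gives no reason for treating statins differently. Pre-admission use cannot stand in for statins first prescribed after the index stroke.

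Any imbalance left after weighting would carry into the adjusted estimates. It would also go unseen, because the check after weighting covers baseline characteristics and discharge statin is not a row in the baseline table.

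**Working it through.** **1. The plan's own counts.** AD yes = 6,075 + 1,072 + 446 = 7,593. AD no = 16,234 + 5,350 = 21,584. The total is 29,177, as stated, with 26.02% treated.

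**2. Size of a possible shift.** The documents give no discharge statin prevalence by group and no statin effect, so all inputs in this step are assumptions: statin hazard ratio g of 0.7 or 0.8, and a residual gap of 5 or 10 points between 75% and 85% use. With p1 the prevalence in AD patients and p0 in no-AD patients, the factor on the AD hazard ratio is (1 + p1(g − 1)) / (1 + p0(g − 1)).

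| p1 vs p0 | g = 0.7 | g = 0.8 |
|---|---|---|
| 85% vs 80% | 0.745/0.760 = 0.980 | 0.830/0.840 = 0.988 |
| 85% vs 75% | 0.745/0.775 = 0.961 | 0.830/0.850 = 0.976 |
| 75% vs 85% | 0.775/0.745 = 1.040 | 0.850/0.830 = 1.024 |

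The largest shift is 0.040 on the log scale and the smallest is 0.012. The limit of about 4% depends on a residual gap of no more than 10 points. A 15-point gap (85% vs 70%) with g = 0.7 gives 0.745/0.790 = 0.943.

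**3. Precision without weighting.** The 95% half-width on the log hazard ratio is 1.96/√(r × 29,177 × 0.2602 × 0.7398). At assumed one-year event rates r of 15%, 30% and 50% this is 0.068, 0.048 and 0.037.

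**4. Precision with weighting, the planned analysis.** The SAP's exposure tables give prior AD use as 5,678 vs 1,836 (yes vs no) in AD patients and 754 vs 20,601 in no-AD patients. Weighting on this covariate alone:

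- P(AD) is 5,678/6,432 = 0.883 in prior users and 1,836/22,437 = 0.082 in the rest.
- Weights in AD patients are 6,432/5,678 = 1.133 and 22,437/1,836 = 12.221. In no-AD patients they are 6,432/754 = 8.531 and 22,437/20,601 = 1.089.
- The weights in each group sum to 6,432 + 22,437 = 28,869.
- The Kish effective size is (sum of weights)² / (sum of squared weights). AD: 28,869²/(7,286 + 274,193) = about 2,960. No AD: 28,869²/(54,868 + 24,437) = about 10,510.
- The half-width is 1.96 × √(1/(2,960r) + 1/(10,510r)).

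| Assumed event rate | Weighted half-width, AD vs none | Unweighted half-width, SSRI (1,072) vs other AD (446) |
|---|---|---|
| 15% | 0.105 | 0.285 |
| 30% | 0.074 | 0.202 |
| 50% | 0.058 | 0.156 |

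**5. Comparison.** The largest shift from the 5 to 10 point range, 0.040, is below the weighted half-width at all three event rates. The smallest, 0.012, is about a fifth of the narrowest. For SSRI vs other AD, even 0.040 is about a quarter of the narrowest half-width (0.040/0.156 = 0.26). Adding further covariates to the weights would normally widen the AD vs none interval further.

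These figures apply to the Cox endpoints. The documents give no spread for home-time, so its shift is not sized here.

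**The case against.** The strongest reply is that the gap is largely covered. Completeness of prescribing is reflected in the other discharge drugs, stroke education, smoking cessation and the hospital variables. Frailty is reflected in age, NIHSS, ambulatory status and discharge disposition. Plausible statin indications such as CAD, diabetes, prior stroke/TIA and PVD are listed. If Table 1 counts as part of the covariate list, dyslipidemia, LDL-C, carotid stenosis and pre-admission cholesterol-reducers are covered too. A crude difference in statin use would then overstate the difference that remains after adjustment. This stands. It is why the gap in the calculation has to be read as a residual one. It does not remove the path through statins newly started at discharge.

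Confounding also needs a link between statin and antidepressant prescribing, and the documents show none. Aim 2 supports only the outcome side. This stands as well, so the estimates can be called open to confounding but not biased.

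Lastly, Other variables reads more like a data inventory than a propensity specification, since it includes discharge antidepressants, which are the exposure. That is a fair criticism and it shapes the fix, but it is not a reason to leave discharge statin out. Over-adjustment is no stronger an argument against statins than against the three discharge drug classes already listed.

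**Conclusion.** The omission is real and of minor priority. The AD vs none comparison is left open to some residual confounding by statins started at discharge, with neither its existence nor its direction established. Under the assumed inputs the hazard ratio would shift by at most about 4%, and for SSRI vs other AD the shift is negligible.

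A reader might infer that the bias is as large as the effects that a 29,177-patient analysis can declare significant. The documents do not support this. That impression comes from the unweighted precision, where the half-width falls to 0.037 at a 50% event rate. The planned estimator is weighted, and the imbalance in prior antidepressant use alone (75.57% vs 3.53%) raises the half-width to between 0.058 and 0.105. A shift of 0.040 would not by itself move the interval off 1, although it could tip a borderline result. Nor is this the main source of confounding: history of depression (43.58% vs 4.78%) and prior AD use differ far more between the groups, and both are already listed.

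The conclusion rests on the assumed statin effect, the residual gap and the event rates, and on an approximate effective sample size from a single covariate.

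**What to change.** - In SAP, Other variables, add statin or other lipid-lowering therapy to the discharge variables.
- In Objective 2, state the selection-model covariates explicitly. Include discharge lipid-lowering therapy, and dyslipidemia and pre-admission cholesterol-reducers from Table 1.
- Exclude discharge antidepressants from that model, since they are the exposure.
- Report the standardized difference for discharge statin before and after weighting. The protocol already names standardized differences as its balance measure.
- If discharge statin is left out on purpose, give the reason in one sentence.

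The cost is one added discharge variable, two rows already in Table 1, and a wording change. That the registry holds discharge statin is an inference from the protocol's planned statin comparison and its description of the form, which does not name statins. It should be confirmed, but no new data collection is expected.
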